## Vernakalant IV Sterile Concentrate Prospective Safety Registry Study

Sponsor Protocol Identifier: 6621-049-00

3 August 2016

---

unique to this technique, including skin burns, complications of sedation and malfunctions of a pacemaker or internal defibrillator. [Ref. 5.4: 104]

The potential adverse events of both electrical and pharmacological cardioversion and the limited efficacy of pharmacological cardioversion have warranted the development of novel therapeutic options. [Ref. 5.4: 371, 441]

Vernakalant, a medicine that acts preferentially in the atria, has a novel and unique mechanism of action. Controlled clinical trials [Ref. 5.4: 441] of vernakalant IV have been conducted to define the efficacy and safety profile of vernakalant IV. Two phase III randomised trials demonstrated that the conversion rate of recent onset ( $\leq 7$  days) AF to sinus rhythm was significantly better for Vernakalant compared to placebo (51.1% versus 3.8%, respectively;  $p<0.0001$ ) with an open-label trial demonstrating a conversion rate of 50.9%. [Ref. 5.4: 442] Another phase III randomised trial of post-cardiac surgery patients (CAD and/or VHD) demonstrated that Vernakalant was significantly better compared to placebo in the conversion of recent onset ( $\leq 3$  days) AF to sinus rhythm (47% versus 14%, respectively;  $p<0.001$ ). [Ref. 5.4: 210] In patients who converted to sinus rhythm, the median time to conversion was 11-13 minutes in those studies.

Clinically significant adverse reactions occurred infrequently. Clinically significant adverse reactions observed in the clinical program and described in detail in the Summary of Product Characteristics (SmPC) included: hypotension, ventricular arrhythmia, atrial flutter and bradycardia. Incidence rates for these adverse reactions are presented below, using pooled data from the placebo-controlled phase 2 and phase 3 clinical trials (773 patients received vernakalant, 335 received placebo). Because vernakalant IV is rapidly cleared from the circulation, adverse events from the start of infusion through the first 2 hours after infusion are considered, as these occur during the period of peak vernakalant exposure.

Adverse Reaction	Vernakalant	Placebo	$\Delta$ (95%CI)
Hypotension	7.6%	5.1%	2.5 (-0.6, 5.6)
CHF subpopulation	16.1%	4.7%	11.4 (3.3, 19.4)
Clinically meaningful hypotension*	1.2%	0%	---
CHF subpopulation	2.9%	0%	---
Ventricular arrhythmia	3.9%	3.2%	0.8 (-1.6, 3.2)

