## **Vernakalant IV Sterile Concentrate Prospective Safety Registry Study**

Sponsor Protocol Identifier: 6621-049-00

3 August 2016

---

\* "Clinically meaningful" events included serious adverse events (SAEs) and events leading to discontinuation of therapy.

In these studies, hypotension typically occurred early, either during the infusion or early after the end of the infusion, and could usually be corrected by standard supportive measures. Ventricular arrhythmias typically presented as asymptomatic, monomorphic, non-sustained (average 3-4 beats) ventricular tachycardias. Bradycardia was observed predominantly at the time of conversion to sinus rhythm. In general, bradycardia responded well to discontinuation of vernakalant and/or administration of atropine.

Due to the higher incidence of hypotension and ventricular arrhythmia in patients with CHF, vernakalant should be used cautiously in haemodynamically stable patients with CHF functional classes NYHA I to II. There is limited experience with the use of vernakalant in patients with previously documented LVEF  $\leq$  35% and its use in these patients is not recommended. The use of vernakalant IV in CHF patients corresponding to NYHA III or NYHA IV is contraindicated.

These clinically significant adverse reactions are being monitored as identified and potential risks in the vernakalant Risk Management Plan (RMP). In addition, although there were no examples of vernakalant IV overdosing in the clinical trials, in consideration of the logistical complexity of weight-based dosing regimens such as that used for vernakalant, potential risk of overdose is also being monitored through the RMP.

Vernakalant IV was approved 1 September 2010 by the European Commission for rapid cardioversion of recent onset AF (<=3 days duration for post-cardiac surgery and <=7 days duration for non-surgical patients).

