4.2 Analysis Populations

All screened patients will be included in summary of patient disposition with additional summary of their demographic characteristics. All enrolled patients who meet the eligibility criteria, sign the informed consent form, and are administered vernakalant IV will be included in the analysis population set, regardless of their disposition status. If a patient's consent is withdrawn prior to completing follow-up period, all data already collected as part of the study will be retained for analysis unless country-specific ethics committee (EC) requirements prohibit this or the patient requests otherwise. In addition, patients who discontinue from the study prior to receiving vernakalant administration will not be included in the overall analysis population. All the summaries will be presented on the overall analysis population set unless otherwise stated.

Patients may be enrolled in the study more than once in association with multiple administrations of vernakalant IV. Patients with multiple enrolments are included in the analysis population, and the number of previous study enrolments is provided in the study analysis. All study analyses presented in the study tables, listings, and figures of this report treat each patient's subsequent administrations of vernakalant IV as occurring independently.

Effectiveness analysis population is defined as all patients from overall analysis population defined above EXCEPT those who receive ECV or IV Class I/III AA for cardioversion within 90 minutes of start of the first vernakalant IV administration. But for analysis of the effectiveness of

vernkalant IV, e.g., rate of conversion, both analysis population and effectiveness population may be used.

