requiring temporary or permanent pacing) will be reported both separately and combined. A study definition of SAEs involving bradycardia is conservatively added to the investigator assessment based on a list of MedDRA terms that would be considered to be SAEs involving bradycardia (**Appendix 2**). Therefore “investigator assessment” includes bradycardia HOIs designated as such per the investigator and/or study definition. MedDRA code version 14.0 used to identify SAEs are consistent with clinical development program.

For patients who receive one infusion during a treatment episode, the follow-up period for HOIs is from the start of this infusion through the first 24 hours, or until discharge/end of medical encounter, whichever occurs earlier.

For patients who receive more than one infusion during a treatment episode, the follow-up period for HOIs is from the start of the first infusion through the first 24 hours following the start of the last infusion, or until discharge/end of medical encounter, whichever occurs earlier.

Because HOIs are expected to be rare events, Clopper Pearson (Exact) confidence intervals will be constructed around the point estimate of the incidence for each HOI. [3] Numbers and rates of HOIs will also be presented according to time intervals since start of first vernakalant infusion, i.e., 0 to less than 2 hours, 2 to less than 4 hours, and 4 hours to a maximum of 24 hours.

The primary analysis for HOI incidence is the 0-2 hour post infusion time point. Given the lower expected sample size, vernakalant's mode of action and the non-interventional nature of the study design, the 2-4 hour and 4-24 hour post infusion time points are considered secondary and tertiary analyses, respectively.

The HOI incidence for each time interval will be calculated as follows.

For each time interval, the numerator will be the number of patients with at least one HOI with an onset date and time in the time interval occurring among patients enrolled and treated with vernakalant. The denominator will be the number of patients enrolled and treated with vernakalant.

For the 0-<2 hour time interval, the number of patients with at least one HOI with an onset date and time in the 0-2 hour interval (interval is from start date and time of vernakalant administration to 1:59:59 following start date and time of vernakalant administration) divided by the number of patients enrolled and treated with vernakalant.

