5.7 Secondary Objective #1: Counts and Rates of Serious Adverse Events (SAEs)

Per Secondary Objective #1, tables with counts and cumulative incidence of SAEs (including HOIs) will be provided and summarised by MedDRA system organ class (SOC), high level term (HLT), and preferred term (PT), and also stratified by outcome (recovered, recovered with sequelae, and not recovered) (**Tables 16.1a.1 to 16.1a.3**), fatal or non-fatal (**Tables 16.1b.1 to 16.1b.3**), and relationship to the study drug (definitely related, probably related, possibly related, probably not related, definitely not related) (**Tables 16.1c.1 to 16.1c.3**). Incidence is calculated as the number of patients who have a SAE starting during the study period, divided by the total number of patients in the analysis population set, times 100.

Characteristics of patients with SAEs, which may include medical history, presenting conditions, medication use, dosing/administration of vernakalant IV, and concomitant therapies, will be summarised in the narrative in a listing of individual SAEs in study reports (**Listing 2b**). Site-reported case narratives and clinical narrative from the medical monitor will be provided for each

SAE. Listings will be by event (i.e., patient with multiple events will be repeated for each event type) and will contain the patient's case narrative for each event.

5.8 Secondary Objective #2: Characterise Patients Administered Vernakalant IV by Medical History, Presenting Conditions and Other Baseline Characteristics

Pertaining to Secondary Objective #2 and Primary Objective #3, the number and percentage of patients greater than 18 years of age (adults) and patients administered vernakalant for recent onset atrial fibrillation (\leq 7 days duration for non-surgical atrial fibrillation and \leq 3 days duration for post-cardiac surgery atrial fibrillation) in accordance with the vernakalant Summary of Product Characteristics (SmPC) will be described (**Table 10**).

In addition, the number and percentage of patients with a reported contraindication for use as specified in the vernakalant IV SmPC will be described (**Table 11**). Specifically, the description will include the following conditions:

- Patients with systolic blood pressure <100 mm Hg
- Acute coronary syndrome (including myocardial infarction) within the last 30 days
- Patients with prolonged QT at baseline (uncorrected > 440 msec) in absence of pacemaker
- Severe aortic stenosis

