|--|---|---------------------------------|----------|--|---------------------------------|----------|---|---------------------------------|----------|--------------------|---------------------------------|----------|
| | 0 - < 2 hours from start of first infusion (N=xxx) | | | 2- < 4 hours from start of first infusion (N=xxx) | | | 4- 24 hours from start of first infusion (N=xxx) | | | Overall (N=xxx) | | |
| Bradycardia Event | Patients n | Incidence (95% CI) ¹ | Events n | Patients n | Incidence (95% CI) ¹ | Events n | Patients n | Incidence (95% CI) ¹ | Events n | Patients n | Incidence (95% CI) ² | Events n |
| Bradycardia following conversion due to vernakalant IV administration ² | xx | x.x (x.x – x.x) | xx | xx | x.X (x.x – x.x) | xx | xx | x.X (x.x – x.x) | xx | xx | x.X (x.x – x.x) | xx |
| Bradycardia following pharmacological cardioversion ³ | xx | x.X (x.x – x.x) | xx | xx | x.X (x.x – x.x) | xx | xx | x.X (x.x – x.x) | xx | xx | x.X (x.x – x.x) | xx |
| Bradycardia following electrical cardioversion ⁴ | xx | x.X (x.x – x.x) | xx | xx | x.X (x.x – x.x) | xx | xx | x.X (x.x – x.x) | xx | xx | x.X (x.x – x.x) | xx |
| Bradycardia Associated with Hypotension ⁵ | xx | x.X (x.x – x.x) | xx | xx | x.X (x.x – x.x) | xx | xx | x.X (x.x – x.x) | xx | xx | x.X (x.x – x.x) | xx |

¹Cumulative incidence calculated as the number of patients who have a specific pre-specified event starting during the study period, divided by the total number of patients enrolled, multiplied by 100.

²Includes all bradycardia SAEs which occurred after the date and time of conversion due to vernakalant IV administration.

³Includes all bradycardia SAEs which occurred after the date and time of pharmacological cardioversion.

⁴Includes all bradycardia SAEs which occurred after the stop date and time of the last shock of electrical cardioversion administration.

⁵Includes all bradycardia SAEs which occurred with hypotension during the same episode.

Template of Table 16.3.1 will be applied to the following two tables.

Table 16.3.2 Incidence of Bradycardia Events of Special Interest by Time since Start of First Infusion – Investigator Assessment (Prospective Patients)

Table 16.3.3 Incidence of Bradycardia Events of Special Interest by Time since Start of First Infusion – Investigator Assessment (Retrospective Patients)

Table 17.1 Non-Serious Adverse Events by System Organ Class (SOC) and Preferred Term (PT) (Final Report) – Analysis Set

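### Table 16.3 divides bradycardia SAEs after conversion, after drug cardioversion and after shock by all enrolled patients, so rows 1-3 are all-patient incidences and not risks after each step

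*SAP*

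**What the plan says.** Table 16.3.1 in SAP Appendix 1 tabulates bradycardia events of special interest by time since first infusion. Under footnote 1 the incidence is the number of patients with an "event starting during the study period, divided by the total number of patients enrolled, multiplied by 100".

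Footnotes 2 to 4 define the numerators of the first three rows: bradycardia SAEs after the time of conversion due to vernakalant (row 1), after the time of pharmacological cardioversion (row 2), and after the end of the last shock of electrical cardioversion (row 3). Row 4, bradycardia with hypotension, needs no such prior step.

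The SAP text never describes Table 16.3; section 5.7 cites only the 16.1 series. Its general conventions use all treated patients. For SAEs in section 5.7 the count is "divided by the total number of patients in the analysis population set, times 100". For HOI intervals section 5.4 says: "The denominator will be the number of patients enrolled and treated with vernakalant". Enrolled and treated are not the same group, because under section 4.2 "patients who discontinue from the study prior to receiving vernakalant administration will not be included in the overall analysis population".

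The Protocol's background section reports conversion on vernakalant "compared to placebo (51.1% versus 3.8%, respectively") in two phase III trials, 50.9% in an open-label trial, and conversion of post-cardiac surgery patients "to sinus rhythm (47% versus 14%, respectively") in a third randomised trial. It also says: "Bradycardia was observed predominantly at the time of conversion to sinus rhythm".

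**The concern.** A patient who never converts on vernakalant cannot score on row 1. One who receives no cardioverting drug in the sense of row 2 cannot score there, and one who receives no shock cannot score on row 3. All of them stay in the denominator. Each printed rate is thus the chance of reaching the step multiplied by the risk after it, while the row label invites a reader to see only the second factor.

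This matters because the Protocol ties bradycardia to the moment of conversion, and Table 16.3 is the only shell that splits bradycardia SAEs by what preceded them. A rarely used procedure will print a low rate simply because few patients had it.

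**Working it through.** **Method check.** Table 16.3.1 is an empty shell, so the nearest stated figure is the worked example in SAP section 4.1: expected proportion 0.003, N = 1,500, limits 0.001 and 0.007, margin 0.004. The Clopper-Pearson limits are the 2.5% quantile of Beta(x, n − x + 1) and the 97.5% quantile of Beta(x + 1, n − x). With x = 0.003 × 1,500 = 4.5 they are 0.0009 and 0.0073, margin 0.0043. This rounds to the stated figures.

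**Relation between the two rates.** With x patients scoring, N in all and m able to score, the printed rate is x/N and the risk after the step is x/m. The ratio is N/m, that is, 1/share.

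**Row 1.** N = 2,000 (SAP section 4.1); conversion rates from the Protocol's background section.

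| Conversion | Can score | Cannot score | N/m |
|---|---|---|---|
| 47% | 940 | 1,060 (53.0%) | 2.13 |
| 50.9% | 1,018 | 982 (49.1%) | 1.96 |
| 51.1% | 1,022 | 978 (48.9%) | 1.96 |

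For an illustrative 10 patients with an event, the printed rate is 10/2,000 = 0.50% (95% CI 0.24 to 0.92). Among converters it is 10/1,022 = 0.98% (0.47 to 1.79) or 10/940 = 1.06% (0.51 to 1.95).

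These are trial rates. If registry conversion were 60% to 70% (an assumption), 30% to 40% could not score and the ratio would be 1/0.7 = 1.43 to 1/0.6 = 1.67.

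**Rows 2 and 3.** The documents give no expected share for either procedure. For an illustrative 4 patients with an event, printed as 4/2,000 = 0.20% (0.05 to 0.51):

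| Assumed share | m | N/m | Rate on m (95% CI) |
|---|---|---|---|
| 10% | 200 | 10 | 2.00% (0.55 to 5.04) |
| 20% | 400 | 5 | 1.00% (0.27 to 2.54) |
| 30% | 600 | 3.3 | 0.67% (0.18 to 1.70) |
| 50% | 1,000 | 2 | 0.40% (0.11 to 1.02) |

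**Comparison across rows.** With these illustrative counts, row 1 prints 0.50% and row 3 prints 0.20%. On the at-risk numbers, with 51.1% converting and 20% shocked, the rates are 0.98% and 1.00%. The printed order carries no information about risk after each step.

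**Related wording in the same shell.**
- The title says Analysis Set, but footnote 1 says enrolled. Read literally, that brings back patients who left before receiving vernakalant.
- The interval in the Overall column carries superscript 2, which is the row 1 definition and not the denominator footnote.
- Footnote 3 does not say whether vernakalant itself counts as pharmacological cardioversion. SAP section 5.9 and Table 12a imply other agents.
- Row 1 needs a conversion time. Protocol section 7.2.1 lists time to conversion among the items that may be missing for retrospective patients, and SAP section 4.4 rules out imputation. Converters without a recorded time would be a further group in the denominator who cannot score.

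**The case against.** The strongest reply is that this is a choice between two valid quantities. Events over all treated patients is a legitimate absolute incidence, it is the convention of SAP sections 5.4 and 5.7, and it keeps Table 16.3 on the same base as the bradycardia rows of the Table 8 series. The title promises incidence by time since first infusion, not risk per route. No objective or analysis text plans to rank routes to sinus rhythm. All of this stands, and it is why the all-patient rate should remain. It does not answer the labelling problem: rows named for what they follow will be read as risk after that step, and the shell gives no number from which to correct the reading.

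A second reply is precision. SAP section 4.3 reserves subgroup HOI rates for groups of, in general, 500 patients or more. At 10% or 20% use the row 3 denominator would be 200 or 400. If Table 16.3.3 rests on the 435 retrospective patients planned in Protocol Appendix I, row 1 would have about 204 to 222 converters (47% to 51.1%), and row 3 about 44 to 131 patients at 10% to 30% use. This is a real cost, but the guide is general and does not bar a descriptive rate with its interval. The SAP already conditions where the quantity is conditional: NYHA class III or IV among patients with a heart failure history (Table 5), drug percentages per IV anti-arrhythmic administration (Table 12a.1), and conversion within the effectiveness population (Table 15a).

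Third, row-specific denominators do not make the rows a fair comparison. Patients shocked after vernakalant are probably mostly those who did not convert on it, time at risk after each step differs, and one SAE can count in several rows. This stands, and the table should say so.

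A reader might also suppose that the at-risk numbers can be taken from other tables. They cannot be taken directly. Table 15a is restricted to conversion within 90 minutes. Tables 12 and 13 use other time windows, and therapies are recorded for up to 7 days after the last infusion, whereas HOI follow-up ends at 24 hours or discharge.

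**Conclusion.** The point holds as one of presentation and interpretation, not as an arithmetic error. Rows 1 to 3 of Tables 16.3.1 to 16.3.3 are all-patient incidences under labels that suggest risk after a step. No other part of the SAP supplies an at-risk denominator, and the rows cannot be compared with one another. For row 1 the printed rate is about half the risk among converters (ratio 1.96 to 2.13), assuming that the trial conversion rates of 47% to 51.1% carry over to the registry.

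Two stronger readings are tempting. One is that about half or more of the patients cannot score on any of the three rows. The documents support this for row 1 only; for rows 2 and 3 it is true only if at most half of the patients have the procedure, and no share is given. The other is that the common denominator will reverse the ranking of vernakalant against electrical or drug cardioversion. That rests on assumed event counts and shares. Even at 10% use the intervals in the example overlap widely (2.00%, 0.55 to 5.04, against 0.98%, 0.47 to 1.79), and no such ranking is planned.

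The table is secondary and descriptive. Primary HOI incidence (Table 8 series) is unaffected. The change is a cheap improvement worth making.

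**What to change.** In Tables 16.3.1 to 16.3.3:

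1. Keep the all-patient rate, with the denominator in footnote 1 changed from enrolled patients to the analysis set (treated episodes).
2. For rows 1 to 3, add the number of episodes with that conversion or procedure after the start of vernakalant and within HOI follow-up, with the rate and Clopper-Pearson interval on that number. Apply the same timing condition to the numerator. Row 4 keeps all treated episodes.
3. Report episodes with missing conversion or procedure times separately.
4. State whether row 2 means agents other than vernakalant.
5. Footnote that one SAE can appear in several rows, and that the rows are descriptive and not a comparison of routes.
6. Correct the superscript in the Overall column.

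This is a shell and programming change. It uses timing fields already collected, where they were recorded, and needs no new data. The cost is wider intervals on smaller denominators, some below the general 500-patient guide of SAP section 4.3, most clearly in Table 16.3.3.

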APPENDIX 2. SERIOUS ADVERSE EVENTS INVOLVING BRADYCARDIA

| Serious Adverse Events | MedDRA PT Term | MedDRA PT Numeric Term |
|--|--|------------------------|
| Verbatim bradycardia terms: | | |
| Bradycardia | Bradycardia | 10006093 |
| Heart rate decreased | Heart rate decreased | 10019301 |
| Electrocardiogram RR interval prolonged | Electrocardiogram RR interval prolonged | 10067652 |
| Bradyarrhythmia SMQ: (standardized Medical Dictionary for Regulatory Activities [MedDRA] Query) | | |
| Accessory cardiac pathway* | Accessory cardiac pathway | 10067618 |
| Adams-Stokes syndrome | Adams-Stokes syndrome | 10001115 |
| Agonal rhythm | Agonal rhythm | 10054015 |
| Atrial conduction time prolongation | Atrial conduction time prolongation | 10064191 |
| Atrioventricular block | Atrioventricular block | 10003671 |
| Atrioventricular block complete | Atrioventricular block complete | 10003673 |
| Atrioventricular block first degree* | Atrioventricular block first degree | 10003674 |
| Atrioventricular block second degree | Atrioventricular block second degree | 10003677 |
| Atrioventricular conduction time shortened* | Atrioventricular conduction time shortened | 10068180 |
| Atrioventricular dissociation | Atrioventricular dissociation | 10069571 |
| Bifascicular block* | Bifascicular block | 10057393 |
| Bradyarrhythmia | Bradyarrhythmia | 10049765 |
| Brugada syndrome* | Brugada syndrome | 10059027 |
| Bundle branch block* | Bundle branch block | 10006578 |

| | | |
|---|--|----------|
| Bundle branch block bilateral* | Bundle branch block bilateral | 10006579 |
| Bundle branch block left* | Bundle branch block left | 10006580 |
| Bundle branch block right* | Bundle branch block right | 10006582 |
| Conduction disorder* | Conduction disorder | 10010276 |
| Electrocardiogram delta waves abnormal* | Electrocardiogram delta waves abnormal | 10014372 |
| Electrocardiogram PQ interval prolonged* | Electrocardiogram PQ interval prolonged | 10053656 |
| Electrocardiogram PR prolongation* | Electrocardiogram PR prolongation | 10053657 |
| Electrocardiogram PR shortened* | Electrocardiogram PR shortened | 10014374 |
| Electrocardiogram QRS complex prolonged* | Electrocardiogram QRS complex prolonged | 10014380 |
| Electrocardiogram QT prolonged* | Electrocardiogram QT prolonged | 10014387 |
| Electrocardiogram repolarisation abnormality* | Electrocardiogram repolarisation abnormality | 10052464 |
| Lenegre's disease* | Lenegre's disease | 10071710 |
| Long QT syndrome* | Long QT syndrome | 10024803 |
| Nodal arrhythmia | Nodal arrhythmia | 10029458 |
| Nodal rhythm* | Nodal rhythm | 10029470 |
| Sick sinus syndrome | Sick sinus syndrome | 10040639 |
| Sinoatrial block* | Sinoatrial block | 10040736 |
| Sinus arrest | Sinus arrest | 10040738 |
| Sinus arrhythmia | Sinus arrhythmia | 10040739 |
| Sinus bradycardia | Sinus bradycardia | 10040741 |
| Trifascicular block* | Trifascicular block | 10044644 |
| Ventricular asystole | Ventricular asystole | 10047284 |

| | | |
|--|--------------------------------|----------|
| Ventricular dyssynchrony* | Ventricular dyssynchrony | 10071186 |
| Wandering pacemaker* | Wandering pacemaker | 10047818 |
| Wolff-Parkinson-White syndrome* | Wolff-Parkinson-White syndrome | 10048015 |
| Bradycardia cases coded with the term: | | |
| Cardiac arrest | Cardiac arrest | 10007515 |

*These terms are included in the definition for SAEs involving bradycardia prior to the interim analyses for 2015, and are not included in the definition for SAEs involving bradycardia thereafter.
